U.S.	United States

PROTOCOL SYNOPSIS

Study Title	Pilot study of loop diuretics among individuals receiving hemodialysis (HD)						
Funder	NIH/NIDDK						
Clinical Phase	Phase II						
Study Rationale	Individuals with end-stage kidney disease (ESKD) receiving HD have high mortality rates driven largely by cardiovascular causes. Volume-related factors including volume overload large interdialytic weight gains (IDWG), and higher ultrafiltration (UF) rates are critical, modifiable contributors to cardiovascular complications such as hypertension, arterial stiffness, left ventricular hypertrophy, and heart failure. Reversing volume overload has been shown to improve blood pressure (BP) and cardiac remodeling, and lower IDWGs and UF rates are associated with lower rates of intradialytic hypotension and less myocardial ischemia on cardiac imaging. While dietary restrictions and longer, more frequent HD can improve these volume-related factors, they add substantial burden for patients. Oral loop diuretics are one potential strategy to increase urine output in HD patients. Loop diuretics are often prescribed for volume control before HD initiation and to patients on peritoneal dialysis. Many, if not most, patients discontinue diuretics once they begin treatment with HD. Small studies suggest that high-dose oral furosemide may increase urine volume in HD patients. However, dose-related side effects raise concern about such doses. Observational data suggest that lower doses of diuretics are associated with both less IDWG and less intradialytic hypotension. Loop diuretic use after HD initiation is associated with lower hospitalization rates. Diuretics may represent a pragmatic, low-cost, and low-burden strategy to improve outcomes in HD patients. Lack of data on optimal furosemide dosing, safety, and acceptability are barriers to expanded use.						
Study Objective(s)	 Primary To generate pilot data on the short-term and longer-term efficacy, safety, tolerability, and acceptability of furosemide in patients with HD-dependent ESKD. Exploratory To generate data on the short-term and longer-term clinical outcomes in patients with HD-dependent ESKD receiving furosemide. 						
Test Article(s)	Oral furosemide (maximum possible dose 320 mg/day)						

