During the 6-week dose escalation period (period 1), participants who are not taking oral furosemide at study entry will take 80 mg oral furosemide twice a day for 14 days and then, if the dose was tolerated, they will take 120 mg oral furosemide twice a day for 14 days and then, if the dose was tolerated, they will take 160 mg oral furosemide twice a day for 14 days. If a patient is taking oral furosemide at study entry, the participant will remain on his/her prescribed oral furosemide dose for the first 2 weeks of the dose escalation period. If a participant is taking another loop diuretic (e.g. bumetanide), we will calculate the corresponding oral furosemide dose (i.e. 1 mg bumetanide = 40 mg furosemide). The participant will discontinue the other loop diuretic and receive the equivalent dose of oral furosemide for the first 2 weeks of the dose escalation period. The first dose will then be increased by 50%, rounded to the nearest whole tablet strength of existing (i.e. available) furosemide tablet formulations (not to exceed 320 mg/day) at week 2 and, if tolerated, the second dose will be increased by 50% at week 4, rounded to the nearest whole tablet strength of existing (i.e. available) furosemide tablet formulations (not to exceed 320 mg/day). Establishing ceiling dose thresholds by increasing the prior dose by 30-50% is the recommended approach in heart failure patients per the American College of Cardiology Foundation/American Heart Association task force on practice guidelines.²⁰ The maximum proposed study dose is 160 mg twice daily (320 mg total per day), which is well below the maximum oral furosemide daily dose of 600 mg/day listed in the furosemide package insert.¹⁹ In addition, the planned furosemide doses are consistent with available formulations (i.e. study doses can be provided using currently marketed furosemide tablet strengths) and standard clinically utilized/approved doses for the FDA-labeled indications. We are not testing higher doses due to the potential increased risk of AEs necessitating drug discontinuation.

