- The investigation does not involve a route of administration, dose, patient population, or other factor that significantly increases the risk (or decreases the acceptability of the risk) associated with the use of the drug product. Specifically, the initial starting dose of oral furosemide in the proposed trial is 80mg twice daily for loop diuretic naïve patients and the maximum proposed study dose is 160 mg twice daily (320 mg total/day). The study doses of furosemide are well below the maximum daily dose specified in the furosemide package insert, 600 mg/day.⁴² Moreover, the proposed furosemide dose escalation scheme is consistent with heart failure guidelines from the American College of Cardiology Foundation/American Heart Association task force on practice guidelines.⁵¹
- The study will be conducted in compliance with Institutional Review Board (IRB) review requirements set forth in 21 CFR Part 56 and informed consent requirements set forth in 21 CFR Part 50.
- The study will be conducted in compliance with 21 CFR 312.7 (i.e. the investigation is not intended to promote or commercialize the drug product).

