1.3 Clinical Data to Date

Heart Failure: Most patients with heart failure and volume overload are initially treated with the combination of an oral loop diuretic (e.g. furosemide) and a low sodium diet. The diuretic response to furosemide is described by a threshold type dose-response curve linking the rate of diuretic excretion in the urine and the degree of natriuresis. There is virtually no increase in natriuresis until the threshold concentration of luminal diuretic is reached and, once the threshold is exceeded, the degree of natriuresis increases until a maximal ceiling is reached.^{22, 23} As the threshold concentration differs across patients, it is necessary to determine an effective dose in individual patients. The usual starting dose in furosemide-naïve patients without kidney dysfunction is furosemide 20 to 40 mg once or twice daily, and subsequent dosing is determined by the diuretic response. It is customary to double the prior dose when titrating furosemide for a diuretic response.²⁰ For patients with normal glomerular filtration rate, maximal single oral doses of furosemide are 40 to 80 mg. For patients with kidney insufficiency (impaired glomerular filtration rate), a higher maximum dose of 160 to 200 mg of furosemide can be given (maximum total daily dose of 600 mg).¹⁹ Dosing in patients who have received prior loop diuretic therapy is based upon the response to prior dosing amounts.²⁰

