- Systolic BP <80 mmHg that a study investigator attributes to study drug-induced hypovolemia

- Patient desires not to continue furosemide
- Patient-reported symptom of severe or very severe
 - Rash
 - Tinnitus
 - Other self-reported symptom plausibly attributed to furosemide
 - Hearing change (also evaluated with the Inner Effectiveness of Auditory Rehabilitation (Inner EAR) instrument*)

*In addition to self-reported hearing change, we will monitor hearing with the Inner EAR instrument. The Inner EAR instrument measures hearing-related function and has good intra-rater reliability, internal consistency, discriminant validity, and responsiveness to change. Instrument scores correlate with pure tone audiometry.³⁸⁻⁴⁰ Scores range from 0 to 100 points. We will refer participants with ≥10-point decline in Inner EAR scores or self-reported hearing loss (any severity) after furosemide initiation and/or dose titration for audiometry testing. Audiometry for all participants is impractical (i.e. expensive, additional clinic visits) and unnecessary given low risk of hearing complications at the proposed doses (maximum 320 mg/ day).³²⁻³⁴

See **Section 7** for additional safety information (e.g. monitoring, adverse events and serious adverse events).

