4.3 Intervention/Treatment procedures (by visits)

During the 6-week dose titration period (period 1), study drug administration visits will occur every 2 weeks on the first day of the participant's weekly, routinely scheduled HD treatments (i.e. Monday or Tuesday during weeks 0, 2, 4, and 6). During the 12-week follow-up period (period 2), study drug administration visits will occur every 4 weeks on the first day of the participant's weekly, routinely scheduled HD treatments (i.e. Monday or Tuesday during weeks 10, 14 and 18).

Dose-titration (period 1)

Week 0:

A. Participants who are not taking oral furosemide at study entry will receive 2-weeks supply of 80 mg oral furosemide twice daily dosing.

- B. Participants who are taking oral furosemide at study entry will receive 2-weeks supply of his/her prescribed oral furosemide dose.
- C. Participants who are taking another loop diuretic (e.g. bumetanide) at study entry will receive 2-weeks supply of an equivalent dose of furosemide (1mg bumetanide = 40 mg furosemide).

Week 2:

- A. Participants who were not taking oral furosemide at study entry and who tolerated the 80 mg twice daily dose (i.e. no hypokalemia, serious hypotension, symptoms, etc.) will receive 2-weeks supply of 120 mg oral furosemide twice daily dosing.
- B. Participants who were taking oral furosemide at study entry and tolerated the first 2 weeks of dosing will receive 2-weeks supply of furosemide dose 50% higher than initial dose, rounded to the nearest whole tablet strength of existing (i.e. available) furosemide tablet formulations (not to exceed 320 mg/day).
- C. Participants who were taking another loop diuretic at study entry and tolerated the first 2 weeks of furosemide dosing will receive 2-weeks supply of furosemide dose 50% higher than their initial dose, rounded to the nearest whole tablet strength of existing (i.e. available) furosemide tablet formulations (not to exceed 320 mg/day).
- D. Participants who did not tolerate the weeks 0 and 1 dose of furosemide will stop furosemide, and it will not be restarted. See below for parameters for determining intolerance.

Week 4:

- A. Participants who were not taking oral furosemide at study entry and who tolerated the 120 mg twice daily dose (i.e. no hypokalemia, serious hypotension, symptoms, etc.) will receive 2-weeks supply of 160 mg oral furosemide twice daily dosing.

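### The stated 320 mg/day maximum is not assured for participants who enter on a loop diuretic: week 0 has no cap, and above 320 mg/day the week 2 step contradicts itself

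*Combined protocol and SAP*

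**What the plan says.** **The maximum.** The synopsis (Test Article) gives "Oral furosemide (maximum possible dose 320 mg/day". Section 1.2 says "The maximum proposed study dose is 160 mg twice daily (320 mg total per day), which is well below the maximum oral furosemide daily dose", and adds: "We are not testing higher doses due to the potential increased risk of AEs necessitating drug discontinuation". The IND-exemption text in the same section repeats that "the maximum proposed study dose is 160 mg twice daily (320 mg total/day" and states: "The study doses of furosemide are well below the maximum daily dose specified in the furosemide package insert, 600 mg/day". Section 1.3.1 calls audiometry for all participants "unnecessary given low risk of hearing complications at the proposed doses", with 320 mg/day given there as the maximum.

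**Participants not on furosemide at entry.** Sections 1.2, 3.5.2 and 4.3 set 80, then 120, then 160 mg twice daily.

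**Participants on a loop diuretic at entry.**
- Week 0 (Section 4.3, item B): "Participants who are taking oral furosemide at study entry will receive 2-weeks supply of his/her prescribed oral furosemide dose". Item C gives users of another loop diuretic the equivalent furosemide dose, at 1 mg bumetanide to 40 mg furosemide. Sections 1.2 and 3.5.2 say the same. None of these places caps the week 0 dose.
- Weeks 2 and 4 (Section 4.3, items B and C): the initial dose raised by half, rounded to available tablets and capped at 320 mg/day. At week 6 the current dose continues under the same cap.
- Weeks 4 and 6, item D: a participant who did not tolerate the current dose goes back to the last tolerated one. No cap is attached.
- Weeks 10 and 14: the maximally tolerated period 1 dose continues. No cap is attached.

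**Eligibility.** Section 3.4 excludes non-loop diuretics. It sets no upper limit on the loop-diuretic dose at entry.

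**The concern.** Study drug is dispensed under Section 4.3, while the safety reasoning follows the maximum in the synopsis and Sections 1.2 and 1.3.1. If the dispensing rule can supply more than the stated maximum, the ceiling that a safety monitor or ethics committee reads is not one the rules deliver.

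There is also a consequence for the analysis. The primary efficacy endpoint (Section 6.1) compares later 24-hour urine volume with the week -1 collection. The protocol describes no washout, so prior users give that baseline sample on their own diuretic. If the week 2 step lowers the dose, the week 5 urine may be taken on less drug than the baseline urine. Section 6.3.4 models the effect of increased dose through a fixed effect of time (dose), which would treat such a person as escalated.

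**Working it through.** **The plan's own figure.** 2 × 160 mg = 320 mg/day, as stated. For participants new to furosemide the daily totals are 160, 240 and 320 mg, with steps of 120/80 − 1 = 50% and 160/120 − 1 = 33%. The maximum holds for them.

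**Prior users.** Let D be the entry dose in mg/day, after conversion if needed.
- Week 0 dose = D (no cap).
- Week 2 dose = the smaller of 320 and 1.5 × D, rounded to 20 mg.
- Week 0 exceeds the stated maximum when D > 320, which is bumetanide above 320/40 = 8 mg/day.
- A full 50% step fits under the cap only when D ≤ 320/1.5 = 213 mg/day.

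The documents do not report entry doses. The values of D below are assumptions, taken up to the 600 mg/day label maximum that the protocol cites.

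| Entry dose D (mg/day) | Bumetanide at 40:1 (mg/day) | Week 0 dose ÷ 320 | Week 2 dose (mg/day) | Change at week 2 |
|---|---|---|---|---|
| 160 | 4 | 0.50 | 240 | +50% |
| 240 | 6 | 0.75 | 320 | +33% |
| 280 | 7 | 0.875 | 320 | +14% |
| 320 | 8 | 1.00 | 320 | 0% |
| 360 | 9 | 1.125 | 320 | −11% |
| 400 | 10 | 1.25 | 320 | −20% |
| 480 | 12 | 1.50 | 320 | −33% |
| 600 | 15 | 1.875 | 320 | −47% |

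For D > 320 the two parts of the week 2 instruction conflict, because 1.5 × D is above 480 while the cap is 320. Only the cap can be applied, and the step becomes a reduction.

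**Return and continuation rules, read literally.** Take D = 400. The participant tolerates 400, is moved to 320 at week 2, and then has an event that counts as intolerance. Week 4 item D sends that person back to the last tolerated dose, which is 400: upward, and above the stated maximum. The weeks 10 and 14 rule carries no cap either.

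**Urine comparison.** With D = 400 and no return, the week -1 urine is taken on 400 mg/day (or its bumetanide equivalent) and the week 5 urine on 320 mg/day, which is 20% less drug.

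**Dosing frequency.** Section 1.2 gives the maximum as 160 mg twice daily, and Section 9.1 describes a twice-a-day medication. The prior-user items in Section 4.3 state a daily cap only, with neither a frequency nor a per-dose figure.

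**The case against.** The strongest reply is that the gap is narrow. For every prior user entering at or below 320 mg/day, the daily maximum holds at each step. Above that, the week 0 dose is the participant's existing prescription or its conversion, not an escalation chosen by the study. The synopsis figure could also be read as a global ceiling over every rule. Entry doses are not given. Section 1.1 puts diuretic use below 25% six months into hemodialysis, though a sample selected for urine output may differ. All this limits how many people are affected. It does not remove the contradiction: a global ceiling would conflict directly with the uncapped week 0 instruction.

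A reader might infer more than the documents support:
- **That the safety case fails for prior users as a group.** It does not. Entry doses from 320 to 600 mg/day do not exceed the label figure, although the margin below it narrows. The oral ototoxicity figure in Section 1.3 is above 800 mg/day. The Inner EAR instrument is given at baseline and on schedule, and a 10-point decline or any self-reported hearing loss leads to audiometry.
- **That the study will give oversized single doses.** An assumed 160 mg once-daily user raised by half would reach 240 mg at once, above the range in Section 1.3, where "a higher maximum dose of 160 to 200 mg of furosemide can be given". But that range is heart-failure background, not an adopted study limit, and the twice-a-day wording points the other way. This is an ambiguity.
- **That two full 50% steps need entry at or below 320/2.25 = 142 mg/day.** That assumes compounding. Sections 1.2 and 3.5.2 suggest it, but week 4 of Section 4.3 counts from the initial dose.
- **That entrants at the cap will be recorded as having tolerated escalation.** No endpoint in Section 6.1 or 6.2 does this. Having no room to rise at 320 mg/day is simply what a ceiling does; it matters only for how dose is read in the models.

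**Conclusion.** The contradiction is real and the text is wrong as written. The 320 mg/day maximum is not assured for participants entering on a loop diuretic, and it is false for anyone entering above 320 mg/day. For those entrants the week 2 instruction cannot be followed as worded, and the cap turns it into a cut of 11% to 47% over assumed entry doses of 360 to 600 mg/day. The uncapped return rule could then raise the dose again.

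The sizes rest on assumed entry doses and a literal reading of the rules. The number affected is unknown and may be zero. The statements that rely on the maximum are unsecured for prior users as a group, not shown to be untrue for them. It remains worth correcting because a stated safety ceiling should follow from the dispensing rules.

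**What to change.** Reconcile the synopsis, Section 1.2 (dosing and IND exemption), Section 1.3.1, Section 3.4, Section 3.5.2 and Section 4.3 (weeks 0 to 6, including item D, and weeks 10 and 14). Either make the week 0, return and continuation rules consistent with the stated maximum, or restate the maximum, and the audiometry and IND-exemption statements that rely on it, to what the rules allow. Clarify whether the maximum for prior users is per day only or also per dose. Which dose or rule applies is for the sponsor to decide.

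In the analysis plan, flag participants whose entry dose leaves no room to escalate, or whose dose falls at week 2, so that the time (dose) term in Section 6.3.4 does not treat them as escalated. The prior-diuretic subgroup in Section 6.3.6 only partly separates them, because it pools all prior users.

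The cost is protocol wording, a look at the entry prescription in the medication review already made at baseline (Section 5.1), and one derived variable. Any effect on who can enter depends on the sponsor's choice.

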4.4 Follow- up procedures (by visit types)

All study visits will occur at the time of routinely scheduled HD treatments at the patient's usual outpatient dialysis clinic. *Section 5* describes the measurements and assessments in detail.

Blood samples (weeks 1, 2, 3, 4, 5, 6, 10, 14, and 18): Blood will be obtained for the measurement of serum sodium, potassium, chloride, urea, creatinine, magnesium, calcium, albumin, and furosemide level. An additional 2.5 mL blood sample will be drawn, frozen, and stored in UNC Kidney Center -80° freezers for future testing as needed.

Urine samples (weeks -1, 5, 12, and 18): 24-hour urine collections will be obtained for the measurement of urine volume, sodium, urea, creatinine, and furosemide level. An aliquot of urine will be taken from the sample after the before-listed measurements are performed and be frozen and stored in UNC Kidney Center -80° freezers for future testing as needed.

Adherence assessments (weeks 1, 2, 3, 4, 5, 6, 8, 10, 12, 14, 16, and 18): Study staff will complete pill counts.

Acceptance assessments (weeks 1, 2, 3, 4, 5, 6, 8, 10, 12, 14, 16, and 18): Study staff will ask the participant the acceptance question.

Symptom assessments (weeks 1, 2, 3, 4, 5, 6, 8, 10, 12, 14, 16, and 18): Study staff will administer surveys evaluating patient-reported cramping, dizziness/pre-syncope, unusual tiredness/weakness, chest pain, rash, nausea, vomiting, diarrhea, tinnitus, hearing change, and numbness/tingling.

Hearing assessments (weeks 2, 4, 6, 10, 14, and 18): Study staff will administer the Inner EAR instrument.

Clinical data (weeks -4 to 18): HD treatment-level data (BPs, weights, dialysis prescription) will be obtained from the EHR.

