4 STUDY PROCEDURES

4.1 Overview (Tables 2 and 3)

All study visits will occur at the participant's dialysis clinic at routinely scheduled HD treatments.

- There will be one study visit during the baseline period.
- Dose escalation period (period 1): Blood samples will be collected weekly at mid-week treatment visits (i.e. Wednesday or Thursday during weeks -1, 1, 2, 3, 4, 5 and 6) prior to scheduled dose initiation or dose titration. Urine samples will be collected twice during the dose escalation period at mid-week treatment visits (i.e. Wednesday or Thursday during weeks -1 and 5). Study drug visits will be conducted every two weeks at the first weekly treatment (i.e. Monday or Tuesday during weeks 0, 2, 4, and 6). This structure was selected so that blood results will be collected and analyzed the week prior to study drug dose titration. As such, test results will be available prior to potential dose titration. Adherence and symptom assessment visits will be conducted weekly at the first treatment of each week (i.e. Monday or Tuesday during weeks 1, 2, 3, 4, 5 and 6). Hearing

assessments will be conducted every two weeks at the first weekly treatment (i.e. Monday or Tuesday during weeks 2, 4, and 6).

- Follow-up period (period 2): Blood samples will be collected at mid-week treatment visits every 4 weeks (i.e. Wednesday or Thursday during weeks 9, 13 and 17). Study drug visits will be conducted at the first treatment of each of the subsequent weeks (i.e. Monday or Tuesday during weeks 10 and 14). As in the dose escalation period, this structure was selected so that blood results will be available prior to additional study drug administration. Study adherence and symptom assessment visits will be conducted every 2 weeks at the first weekly HD treatment in the scheduled week (i.e. Monday or Tuesday during weeks 8, 10, 12, 14, 16, and 18). Hearing assessments will be conducted every four weeks at the first weekly treatment (i.e. Monday or Tuesday during weeks 10, 14, and 18). Urine sample visits will be conducted at the mid-week treatments of the 12th week and final week of the follow-up period (i.e. Wednesday or Thursday during weeks 12 and 18). All remaining study drug will be returned at the first weekly treatment (i.e. Monday or Tuesday) of week 19. A final pill count (adherence assessment) will be performed upon study drug return (week 19).

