- All HD treatments occurring during the 18-week study period will be considered study treatments, and all associated clinical data (BP, pre-HD and post-HD weights and dialysis treatment data such as UF volume, UF rate and dialysate composition) will be collected from the electronic health record (EHR).

Table 2. Study visits by	y type.								
Procedures	Baseline clinical assessment (Prior to study start, weeks -4 to -2)	Baseline electrolyte, urine, symptom, and hearing assessment (week -1)	Study drug visit (weeks 0, 2, 4, 6, 10, 14,)	Follow-up blood sample (weeks 1, 2, 3, 4, 5, 6, 9, 13, 17)	Follow-up urine sample (weeks -1, 5, 12, and 18)	Adherence and symptom assessment (weeks 1, 2, 3, 4, 5, 6, 8, 10, 12, 14, 16, and 18)	Hearing assessment (weeks 2, 4, 6, 10, 14, and 18 weeks)	Clinical data collected at every HD treatment during study period (weeks -4 to 18)	Study drug return (week 19)
Complete medical history	х								
Pregnancy status inquiry	Х								
Serum electrolytes and furosemide level		х		х					
24-hour urine		Х			Х				
Symptom assessment		Х				Х			
Hearing assessment		Х					х		
Study drug administration			Х						
Patient acceptance assessment									
Drop-out rates	Х							х	
Pill counts						Х			Х
End of trial study drug return									Х
BP monitoring	Х							х	
Weight monitoring	Х							х	
UF volume/rate	Х							Х	
Extra HD treatments	Х							х	
Hospitalizations	Х							х	

Table 2. Stud	Table 2. Study visits by week.																					
Week(s)	-4 to -2	-1	0	1	2	3	4	5	6	7	8	9	10	11	12	13	14	15	16	17	18	19
Procedures																						
Complete	Х																					

medical history																						
Pregnancy status inquiry	Х																					
Serum electrolytes and furosemide level		x		x	x	x	x	x	х			x				x				x		
24-hour urine		Х						Х							Х						Х	
Symptom assessment		х		х	х	х	х	х	х		х		х		х		х		х		х	
Hearing assessment		х			х		х		х				х				х				х	
Study drug administration			х		х		х		х				х				х					
Patient acceptance assessment				х	х	х	х	х	х		х		х		х		х		х		х	
Drop-out rates	Х	Х	Х	Х	Х	Х	Х	Х	Х	Х	Х	Х	Х	Х	Х	Х	Х	Х	Х	Х	Х	
Pill counts				Х	Х	Х	Х	Х	Х		Х		Х		Х		Х		Х		Х	Х
Study drug return																						Х
BP monitoring	х	x	x	х	х	х	х	х	х	х	х	х	х	х	х	х	х	х	х	х	х	
Weight monitoring	Х	х	х	х	х	х	х	х	Х	Х	х	х	х	х	х	Х	х	х	х	х	х	
UF volume/ rate	Х	Х	Х	Х	Х	Х	Х	Х	Х	Х	Х	Х	Х	Х	Х	Х	Х	Х	Х	Х	Х	
Extra HD treatments	Х	х	х	х	х	х	х	х	х	х	х	х	х	х	х	х	х	х	х	х	х	
Hospitalizations	Х	Х	Х	Х	Х	Х	Х	Х	Х	Х	Х	Х	Х	Х	Х	Х	Х	Х	Х	Х	Х	

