acceptance (defined as the patient reporting unwillingness to take the study drug). If one of these events occur, the participant will return to the prior tolerated oral furosemide dose. If one of these events occurs at the lowest administered dose, oral furosemide will be stopped and not re-started.

The window for each dose-titration period intervention/treatment visit is -4 to +4 days.

Follow-up (period 2)

Weeks 10 and 14: Participants who tolerated (i.e. no hypokalemia, serious hypotension, symptoms, etc.) and accepted furosemide in period will continue their maximally tolerated period 1 dose during the 12-weeks of follow-up. At weeks 10 and 14, they will receive additional 4-weeks supplies of this furosemide dose.

As specified in **Section 1.3.1**, if a participant has electrolyte abnormalities or other side effects attributable to furosemide in period 2 (i.e. on their period 1 maximally tolerated dose), the dose will be lowered sequentially (i.e. dose de-escalation: $160 \rightarrow 120 \rightarrow 80$ mg twice daily, or, if on alternative dosing due to prior diuretic use, decrease dose by 50%, rounded to the nearest whole tablet strength of existing (i.e. available) furosemide tablet formulations, until tolerated). If side effects persist or if the participant chooses, oral furosemide will be stopped.

Week 19: At the first weekly treatment (i.e. Monday or Tuesday) of study week 19, participants will return all unused study drug to a study coordinator.

The window for each follow-up period intervention/treatment visit is -4 to +4 days.

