5 STUDY EVALUATIONS AND MEASUREMENTS

5.1 Measurements

All study evaluation and measurements will occur at study visits that occur at the time of routinely scheduled HD treatments at the patient's usual outpatient dialysis clinic. *Section 4.4* describes the timing and frequency of the measurements.

Baseline measurements

Complete medical history and clinical data: The participant's medical history will be taken from the EHR and confirmed verbally with the patient. The medical history will include a review of co-morbid conditions, medications, recent laboratory results (electrolytes, albumin, complete blood count, Kt/V, iron stores, bone-mineral tests), and dialysis treatment data (BPs (systolic and diastolic), weights (pre- and post-HD), UF volumes/rates, dialysate composition (sodium, potassium, bicarbonate, calcium), dialysate and blood flow rates, and vascular access type.

Serum blood tests: The following tests will be assessed via blood samples: sodium, potassium, chloride, urea, creatinine, magnesium, calcium, albumin and serum furosemide level. An additional 2.5 mL blood sample will be drawn, frozen, and stored in UNC Kidney Center -80° freezers for future testing as needed. Blood samples will be collected via the vascular access by trained dialysis clinic personnel.

24-hour urine collection: The following tests will be assessed via 24-hour urine collections: urine volume, sodium, urea, creatinine, and urine furosemide level. An aliquot of urine will be taken from the sample after the before-listed measurements are performed and be frozen and stored in UNC Kidney Center -80° freezers for future testing as needed. Urine samples will be collected by the patient in 24-hour urine collection containers. Containers will be provided by and returned to study staff at the dialysis clinic at specified study visits.

Symptom assessment: Study staff will administer a symptom questionnaire (*Appendix, Section 13.1*) to participants at specified study visits.

Hearing assessment: Study staff will administer the Inner Ear instrument (*Appendix, Section 13.2*) to participants at specified study visits.

Follow-up measurements

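### Section 4.4 dates the period 2 blood samples one week later than Section 4.1 and both visit tables; at nominal visit days this removes the stated electrolyte check before resupply at weeks 10 and 14

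*Combined protocol and SAP*

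**What the plan says.** All references are to the combined protocol and SAP.

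- **Section 4.4** lists "Blood samples (weeks 1, 2, 3, 4, 5, 6, 10, 14, and 18", with no weekday. Section 5.1 points to 4.4 as the section that "describes the timing and frequency of the measurements".
- **Section 4.1**, for period 2, says "Blood samples will be collected at mid-week treatment visits every 4 weeks (i.e. Wednesday or Thursday during weeks 9, 13 and 17".
- **Table 2, by visit type**, has the column "Follow-up blood sample (weeks 1, 2, 3, 4, 5, 6, 9, 13, 17".
- **Table 2, by week**, has a row "Serum electrolytes and furosemide level" with period 2 marks in weeks 9, 13 and 17 and none in weeks 10, 14 or 18.
- **Period 2 drug visits** in 4.1 fall at the "first treatment of each of the subsequent weeks (i.e. Monday or Tuesday during weeks 10 and 14". The visit detail in 4.3 agrees: "At weeks 10 and 14, they will receive additional 4-weeks supplies of this furosemide dose".
- **Purpose.** Section 4.1 states that "this structure was selected so that blood results will be available prior to additional study drug administration".

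**The concern.** These samples supply the longer-term primary safety endpoints of Section 6.1 for potassium, magnesium, corrected calcium and serum furosemide. Each of the three period 2 draws has two different dates, and the section that staff are sent to for timing is the one that disagrees with the other three statements.

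Two things are at stake. First, 4.1 gives a safety reason for drawing blood in the week before a drug visit, and the 4.4 weeks do not serve it. Second, Section 6.3.7 plans a sensitivity analysis that drops participants' data when endpoints, serum electrolytes among them, were collected off-schedule. With two schedules, that rule has no single meaning for period 2 bloods.

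**Working it through.** **Which weeks**

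| Place | Period 2 blood weeks |
|---|---|
| 4.1 text | 9, 13, 17 (Wednesday or Thursday) |
| Table 2 by visit type | 9, 13, 17 |
| Table 2 by week | 9, 13, 17 (22 columns and 22 cells in the electrolyte row, so the marks can be placed) |
| 4.4 | 10, 14, 18 (no weekday) |

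The monthly frequency in 7.7 and the 4-week frequency in 9.1 fit either list. The week 18 assessments listed in 4.5 include no blood sample, which fits the tables. The other timed lines of 4.4 (urine, pill counts, acceptance, symptoms, hearing) agree with the by-week table, so the conflict is confined to the blood line and is not a loss in text extraction.

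**Day arithmetic**

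Day = 7 × week + weekday, with Monday 0, Tuesday 1, Wednesday 2, Thursday 3. Drug visits are at the first weekly treatment and bloods at the mid-week treatment, both from 4.1. The mid-week rule is applied to both lists because 4.4 gives no weekday. For a Monday/Wednesday/Friday patient:

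- *Week 10 resupply*: day 7 × 10 + 0 = 70.
  - Weeks 9/13/17: latest blood is day 7 × 9 + 2 = 65, so 70 − 65 = **5 days old**.
  - Weeks 10/14/18: latest earlier blood is week 6, day 7 × 6 + 2 = 44, so 70 − 44 = **26 days old**. The week 10 blood is day 72, which is 72 − 70 = **2 days after** resupply.
- *Week 14 resupply*: day 98.
  - Weeks 9/13/17: 98 − 93 = 5 days old.
  - Weeks 10/14/18: 98 − 72 = 26 days old; the week 14 blood is day 100, 2 days after resupply.
- *Tuesday/Thursday/Saturday patient*: every day number rises by 1, so the differences are unchanged.
- *Period 1 for comparison*: the week 6 drug visit is day 42 and the week 5 blood is day 37, a lead of 5 days. Weeks 2 and 4 give the same.
- *First period 2 check after the week 6 sample*: 65 − 44 = 21 days (3 weeks), against 72 − 44 = 28 days (4 weeks).

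**Visit window**

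Section 4.3 allows −4 to +4 days for a treatment visit. On the 4.4 weeks, the day 72 blood comes before the drug visit only if that visit runs 3 or 4 days late (day 73 or 74). On weeks 9/13/17, the earliest drug visit in the window is day 70 − 4 = 66, still after a nominal blood on day 65.

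**If 4.4 bloods were drawn at the dispensing treatment itself**

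Section 5.2 sends samples to the laboratory on the day of the draw, and no turnaround time is given. If the result is not back before drug is handed over, the latest earlier one is 26 days old (mid-week sample in week 6) or 28 days old (70 − 42, or 98 − 70).

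**Off-schedule**

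The lists differ by 7 days at each of 3 draws. No window is stated for bloods. Even if the 4-day treatment-visit window were borrowed, 7 > 4, so a draw on its nominal day under one list is off-schedule under the other. With 30 participants in period 2, that is 3 × 30 = 90 planned draws.

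**The case against.** The best case on the other side is that this is one clerical line. Three of four statements agree, 4.1 gives the reason for its timing, and the trial is run at one centre with several clinics, where the principal investigator requests each supply (3.5.3). That makes confusion less likely. It does not settle the matter, because 5.1 names 4.4 as the source and no order of precedence is given.

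The rest of the case limits the consequences, and it stands:

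- **Dose review.** A reader might infer that period 2 dose review as a whole would run on out-of-date electrolytes. The documents do not support that. Sections 3.5.2 and 4.3 tie period 2 dose reduction to the abnormality, not to the resupply visit, and 7.7 has the investigators manage study drug directly, with a recheck within one week. The draws are 4 weeks apart on either list; only the first interval lengthens.
- **Age of results.** The 26 days is the age of the latest study sample. Section 7.3.2 notes that this population has frequent laboratory testing, so other results may exist, although no text says that they inform resupply.
- **Week 18.** A reader might infer that all three draws lose a check before resupply. Section 4.1, both tables and the 4.3 visit detail have no resupply in week 18; only the 4.3 introduction lists a drug visit then.
- **Order of events.** The 2-day reversal takes its weekday from 4.1, and a late drug visit within the window can undo it.
- **Endpoints.** A reader might infer bias in the longer-term safety endpoints. They are incidences over period 2 with three draws on either list, and nothing in the documents allows an effect of a one-week shift to be estimated.

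**Conclusion.** The contradiction is certain. Its safety consequence is specific: if the 4.4 weeks are followed with mid-week draws and nominal visit days, the electrolyte check that 4.1 intends before the week 10 and week 14 resupplies is lost, and the latest study result is 26 days old instead of 5. The first period 2 sample also comes a week later. These figures rest on 4.1's weekday rules and on visits kept to nominal days.

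The analytic consequence needs no weekday assumption: until one list governs, off-schedule cannot be applied to period 2 electrolytes in 6.3.7. The finding does not show harm to participants, divergent practice between clinics, or bias in a primary endpoint.

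**What to change.** 1. Reconcile 4.4 with 4.1 and both tables headed Table 2, so that one list of period 2 blood weeks governs. Because 5.1 relies on 4.4, it then carries the same list.
2. Check the list adopted against 4.1's own purpose of having results before each resupply.
3. In the same edit, reconcile the 4.3 introduction, which lists period 2 drug visits in weeks 10, 14 and 18, with 4.1, the tables and the 4.3 visit detail, which list only weeks 10 and 14.
4. Define off-schedule in 6.3.7 for period 2 electrolytes by reference to that list, with any permitted window.

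The cost is protocol wording. The number of blood draws per participant is unchanged.
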